#### APPENDIX 5:

#### A. Identification of HLA-A2+ individuals by flow cytometry.

[figure not shown]
Cells were incubated in cell culture supernatant from the hybridoma B7.2; washed, incubated with FITC goat anti-mouse antibody (DAKO), washed and fixed in 2% paraformaldehyde. Flow cytometry was performed on a FACScan and analysed using CELLQuest software.

HLA-A2 positive individuals show a shift in fluorescence of at least 1 log

B. Enumeration of *M. tuberculosis* and HIV peptide-specific cells in pleural fluid from an HIV-infected patient with pleural tuberculosis; HLA class I haplotype HLA-A2.

Pleural fluid mononuclear cells were separated on Histopaque (Sigma) and stored in liquid nitrogen until analysed. The IFN- $\gamma$  ELIspot was conducted in a 96 well filtration plate (Millipore Multiscreen) using anti-IFN- $\gamma$  antibodies supplied by MABTECH. Briefly the plate was wetted with alcohol, coated with capture antibody, washed with RPMI and blocked with culture medium (RPMI containing 10% human serum). Cells were thawed, suspended in culture medium and added to the plate at 500,000 cells per well, in a final volume of 200 µl. Wells were stimulated in duplicate with pooled *M. tuberculosis* peptides, pooled HIV peptides, (each peptide at a final concentration of 10 µg/ml) or left unstimulated, and incubated for 24 hours at 37  $^{0}$ C with 5% CO2. The cells were then washed off and the plate was developed with biotinylated second antibody, followed by streptavidin-alkaline phosphatase and then chromogenic substrate (BioRad). Development was stopped with tap water. The plates were dried overnight and spots counted using a dissecting microscope.

SCFs : spot forming cells

Pleural fluid cells from an HIV+, HLA-A2+ Ugandan patient show a positive IFN-γ response for pooled peptides of both *M. tuberculosis* and HIV. Peptides selected on predicted HLA-A\*0201 binding motif. TB peptides: from antigen 85 C. RLRSAATTL AIAAMGAVL **GLPVEYLQV SMSGGSALI PMVOIPRLV** RLVANNTRI **QLVAMKADI** AMKADIQHV HIV peptides: **SLYNTVATL** gag p17, clade D gag p17, clade A **SLFNTVATL** pol, clade D **ILKEPVHGV ILKDPVHGV** pol, clade A (anchor residues for HLA-A\*0201 in bold)

# APPENDIX 6: Time-line of the proposed study.

	Year	1	Year	· 2	Y	ear 3	Y	ear 4	Year	5
Administration & preparations	
 
* Renovations
 
* Ordering
 
* Lab set-up
 
* Staff recruitment
 
* Sensitise community
 
									
Cohort Study, Original plan.		Er	rolment of j	participa	nts		Continu	iing follow	սթ	
Cohort Study, Revised plan.	en		Enrolment of par			ants	Co	ontinuing follow	v up	
Analysis		Pilot: screen -ing data	Pilot: screen -ing immuno -logy	Pilot: maternal & birth outcome & immuno	Main cohort: Interim analysis for maternal	Pilot: outcome in babies at 1 year	Main cohort: Interim analysis of effects of maternal helminths on outcomes at 1	Plans to be	based on earlier an	nalyses
				-logy @ delivery	and birth outcome		year			

#### **APPENDIX 7. MATERNAL AND BIRTH OUTCOMES**

#### **DEFINITIONS.**

Stages of pregnancy: First trimester:	less than 14 weeks
Second trimester	14 to 27 weeks
Third trimester	28 weeks or more

#### Major congenital abnormalities:

Structural or functional defects that require surgical or medical intervention; including but not restricted to the following. Nervous system: anencephaly Dandy-Walker cysts Encephalocele Hydrocephalus Meningomyelocele Microcephaly Cardiovascular system Atrial septal defect Fallot's tetralogy Patent ductus arteriosus Ventricular septal defect *Gastrointestinal tract* Cleft lip Cleft palate Imperforate anus Pyloric stenosis Genitourinary tract chordae of the penis cliteromegaly cyst of hydrocele hypospadias micropenis undescended testis vaginal polyps Musculoskeletal system and skin arachnodactyly congenital dislocation of the hip club foot deletion of fingers or toes micrognathia pholcomalia neonatal teeth polydactyly rudimentary external ears umbilical hernia Dysmorphic features mongoloid features a combination of two or more of ear tags, low hairline, low-set ears, palmar triradius Multisystem abnormalities

abnormalities involving 2 or more of the listed systems prune-belly syndrome Turner's syndrome

Birth weight:	Low birth weight Very low birthweight	<2500 g <1500 g	
Perinatal death:	Stillbirths and all deaths durin	ng the first week from delivery.	
Maternal death:	Death while pregnant or within 42 days of the termination of the pregnancy.		
Severe postpartum	maternal anaemia: <9 g/dl 	3	
Pre-eclampsia	Hypertension (diastolic press and proteinuria ( $\geq$ 2+ on dipst	ure $\geq$ 95, and/or systolic pressure $\geq$ 160 mmHg) ick)	

# **OUTCOMES AT DELIVERY**

1. Outcome: birth outcome	
Measures:	Likely incidence:
major congenital defect	1-2%
stillbirth	1-4%
perinatal deaths	1-7%
low birthweight	18%
very low birthweight	1-2%

#### *Sample size calculations: risk ratio of 2; P=0.05; 80% power.*

Incidence of 1 vs 2%, e.g. major congenital defects; require 2514 in each group; not feasible Indicence of 2 vs 4%, e.g. stillbirths + early neonatal deaths, require 1239 in each group; feasible by end of study Incidence of 10 vs 20%, e.g. low birthweight, require 219 in each group; feasible for interim analysis

#### **Potential confounders / explanatory variables:**

#### **Demographic/ socioeconomic**

education of mother & father literacy of mother & father occupation of mother & father housing type property/ items owned tribe

#### Clinical

mother's height mother's weight at first visit duration of gestation at first visit mother's gravidity past obstetric history alcohol smoking mother's general health (nutrition, diabetes etc) medicines taken during pregnancy illnesses for which medicines taken maternal syphilis maternal HIV

#### 2. Outcome: maternal outcomes

Measures:	Likely incidence:		
Severe postpartum anaemia	8%		
Eclampsia /pre-eclampsia	1-2%		
Mortality	<1%		

#### Confounders / explanatory variables in addition to those considered above:

# Helminth risks sanitation

water source wearing of shoes

#### Clinical

Malaria in pregnancy -film at enrolment - mother and placental film at delivery Malaria risk: environment, bednets, spraying Use of antimalarials in pregnancy Use of antihelminthics in pregnancy Haemoglobinopathies - may be possible to evaluate on stored samples

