#### **Procedures**

#### Mothers: enrolment visit.

Women will be invited to participate in the study at their first antenatal visit if their normal residence is in the proposed study area (Entebbe Municipality; women from the additional, adjacent part of Katabi will be included later if necessary to maintain recruitment rates). Mothers who feel unable to decide to join the study at their first visit to the antenatal clinic, but who wish to do so at later visits, will be accepted provided that they accept all the study procedures, particularly the need for a blood draw on the day of screening.

They will be excluded if they have a history of adverse reactions to anti-helminthic drugs.

They will be excluded if, in the opinion of the doctor or midwife, the current pregnancy is not normal. Normal pregnancies would include twins. Abnormal pregnancies would include, for example, those in which the mother has gestational diabetes, pre-eclampsia or vaginal bleeding.

They will be excluded if they have already participated during an earlier pregnancy within the duration of the study. (Inclusion of more than one pregnancy and child for the same mother would complicate analysis, and the mother's behaviour with regard to antenatal care and use of antihelminthics for herself and her child might be influenced by earlier participation in the study.)

They will be asked to give informed consent for participation in the study of albendazole in pregnancy, and for follow up of the babies to one year of age.

A questionnaire regarding demographic and socio-economic details, clinical history and examination will be completed.

They will have blood drawn for full blood count, malaria slide, examination for microfilariae, HIV and syphilis serology and studies of the maternal immune response (30 ml).

Urine will be examined for protein and glucose using a dipstick.

They will be asked to provide a stool sample.

They will be provided with haematinics and antimalarial prophylaxis (an initial dose of Fansidar). Women with positive syphilis serology (RPR and TPHA) will be treated.

Tetanus immunisation will be given.

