# APPENDIX 2:

#### A. Mothers delivering at Entebbe Grade B Hospital, January 2001.

Data regarding permanent residence and antenatal attendance were obtained from mothers who delivered their babies during a 4 week period in January 2001. Mothers who delivered their babies in the private wing were not included. The findings were as followed.

•	Number of mothers who delivered	106	
٠	Number interviewed	99	
٠	Number (%) with permanent residence in proposed study area	70	(71%)
٠	Number (%) of those from study area who have attended		
	Entebbe Hospital Antenatal Clinics (EH-ANC)	65	(93%)
٠	Mean number of EH-ANC visits (range)	5	(1-16)

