#### Sample size calculation: risk ratio of 2; P=0.05; 80% power.

Incidence of 1 vs 2%, e.g. pre-eclampsia; require 2514 in each group; not feasible Incidence of 5 vs 10%, e.g. postpartum anaemia, require 474 in each group; feasible for interim analysis

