#### a. Clinical findings in mothers and baby at delivery.

Approximately October 2003-January 2004. Analysis period: (When enrolment to the study has completed one year). Clinical and laboratory (haematological and parasitological) results. Data to be analysed: Purpose of analysis: To obtain preliminary data on the effect of albendazole and praziguantel on outcome at delivery for mother and baby, in particular: • maternal post-partum haemoglobin maternal and cord blood viral load in HIV-positive mothers •

- maternal parasite burden •
- eclampsia/ pre-eclampsia\*
- maternal deaths\*
- babies' birth weight
- congenital abnormalities\*
- stillbirths and early neonatal deaths\* •

Access to unblinded data required. \*\*

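### Appendix 7's covariate lists for postpartum anaemia omit enrolment haemoglobin and mix in delivery malaria films; its outcome form differs from Appendix 9's; and its 474 per group needs near-complete uptake in one year

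*Protocol*

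**What the plan says.** Appendix 7 gives two sets of explanatory variables: one for birth outcomes, and a further one for maternal outcomes that adds to the first. Together they run from parental education and housing to footwear and possible haemoglobinopathy testing. Neither names haemoglobin or anaemia at enrolment. The second includes "Malaria in pregnancy -film at enrolment - mother and placental film at delivery".

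The enrolment visit does supply the missing variable: "They will have blood drawn for full blood count, malaria slide, examination for microfilariae". The same result is used to exclude severely anaemic women from randomisation, and the count is repeated at delivery.

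The outcome takes two forms. Appendix 7 defines severe postpartum "maternal anaemia: <9 g/dl" and sizes it under "Sample size calculation: risk ratio of 2; P=0.05; 80% power", concluding: "Incidence of 5 vs 10%, e.g. postpartum anaemia, require 474 in each group; feasible for interim analysis". Appendix 9, main study analysis (a), names "maternal post-partum haemoglobin" instead. It does not carry the asterisk that marks measures likely to lack sample size at that point. That analysis is timed "When enrolment to the study has completed one year".

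Recruitment figures stand in two places. The section on establishing the cohort gives 1200 to 1500 deliveries a year, about 70% to residents of the area, of whom over 90% attend the antenatal clinics. Appendix 2A gives the survey: "Data regarding permanent residence and antenatal attendance were obtained from mothers who delivered their babies during a 4 week period". It counted 106 deliveries; 99 mothers were interviewed, 70 were resident and 65 of those had attended.

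**The concern.** The baseline value of an outcome is usually among its best predictors. A covariate list this detailed that leaves it out gives up precision for nothing. The Ethical Considerations section treats less hookworm-related anaemia as the one established benefit of treatment in pregnancy, so the loss falls on a comparison that readers will look for.

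Delivery films raise a different issue. The protocol itself argues that helminths, and so their treatment, may alter malaria. If delivery malaria were adjusted for when estimating the treatment effect, part of that effect could be removed or distorted. The list does not say which variables serve which analysis.

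Finally, an interim analysis described as feasible at 80% power should be reachable from the stated recruitment. If it is not, an inconclusive early result could be misread as evidence of no effect.

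**Working it through.** **1. The plan's own figure.** Inputs from Appendix 7: 5% vs 10%, P=0.05 (taken as two-sided), 80% power, equal groups.

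- Without continuity correction: n = [1.96·√(2·0.075·0.925) + 0.8416·√(0.05·0.95 + 0.10·0.90)]² / 0.05² = (0.7301 + 0.3121)² / 0.0025 = 434.4, so 435.
- With correction: (434.4/4)·[1 + √(1 + 4/(434.4·0.05))]² = 473.6, so 474.

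The 474 per group (948 in all) is right, with the continuity correction.

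**2. Supply in one year.** The share resident and attending is 0.70 × 0.90 = 0.63 from the text (a floor, since attendance is over 90%), or 65/99 = 0.657 from the survey. Surveyed volume is 106 × 13 = 1378 deliveries a year. Uptake here means consent, no exclusion, delivery in hospital and blood taken before discharge. The protocol gives no rate for it, so 80% is an assumption. Power is for 5% vs 10%, Φ[(0.05·√n − 0.7301)/0.3708]. The corrected value, in brackets, replaces n by (n − 20)²/n.

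| Deliveries × share | Women | Per group, 100% | Power | Per group, 80% | Power |
|---|---|---|---|---|---|
| 1200 × 0.63 | 756 | 378 | 74.3% (69.6%) | 302 | 64.7% (58.7%) |
| 1378 × 65/99 | 905 | 452 | 81.6% (78.0%) | 362 | 72.5% (67.5%) |
| 1500 × 0.63 | 945 | 472 | 83.2% (79.9%) | 378 | 74.3% (69.6%) |
| 1500 × 65/99 | 985 | 492 | 84.7% (81.6%) | 394 | 76.0% (71.6%) |

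Only the last row reaches 474, and it needs 948/985 = 96% of eligible women. On the uncorrected 435 per group, the surveyed volume also needs 870/905 = 96%.

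**3. Timing.** Late enrollees may not have delivered by the analysis. If only deliveries within the enrolment year counted, with an assumed three-month gap from enrolment to delivery, the 100% column falls by a quarter, to 284 to 369 per group.

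**4. Continuous haemoglobin.** If haemoglobin is normal with equal SD and treatment shifts every mother alike, 5% vs 10% below a cut-off is a shift of 1.645 − 1.282 = 0.363 SD. Then n = 2·(2.8016/0.363)² = 119 per group. Adjusting for the enrolment value multiplies this by (1 − r²). At r = 0.5 that is about 89 (90 rounded up); for r = 0.3 to 0.6 it is 109 down to 77. The SD cancels; the uniform shift and r are assumptions.

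**The case against.** Four points can be made for the plan.

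- A reader might infer that anaemia will be analysed only as yes or no. The protocol does not say so: Appendix 9 names post-partum haemoglobin for the same analysis. On step 4's assumptions that measure is well powered at one year, which fits the missing asterisk. What stands is that the two appendices differ.
- A reader might also infer that the randomised comparison will be adjusted for delivery malaria and so biased. No section says this. Appendix 4 defines the overall albendazole contrast as a direct comparison and names no covariates for it, and the films have a natural use in the observational aims. Yet Appendix 4 does adjust its comparisons by infection and treatment status for helminths found at delivery, so adjustment for delivery-time variables is not foreign to this plan and the ambiguity is worth removing.
- Nor is it true that one year cannot supply 474: the top of the stated range does. The Private Wing and the adjacent part of Katabi could add women, in numbers not given. The 70% is quoted for Entebbe Municipality and Katabi together, so some of that area may already be counted.
- Covariate choice is often left to a SAP, which is not at hand, and omitting a prognostic covariate does not bias a randomised comparison. But the protocol does set out a list, in detail, and the loss of precision is avoidable.

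It also counts in the plan's favour that the outcome is not a principal one, that the interim is described as preliminary, and that the full cohort (about 1250 per group) would have over 99% power for 5% vs 10%.

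**Conclusion.** The point holds in limited form and should be corrected. Enrolment haemoglobin is missing from the lists though it is measured in every mother. Delivery malaria films are listed without being separated from baseline variables. Appendices 7 and 9 use different forms of one outcome for one analysis. These three rest on the text alone.

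The feasibility statement is optimistic rather than impossible. At full uptake the shortfall is small, and at the surveyed volume power is 82% without the continuity correction. It becomes material at about 80% uptake, where power is roughly 65% to 76% (59% to 72% corrected). That rests on the assumed uptake and on no added recruitment source.

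The saving from a continuous analysis should be read with care. The protocol expects benefit through hookworm, with a minimum prevalence of 18% in Appendix 2B, and excludes women at or below 8 g/dl. An effect concentrated in a minority need not move the overall mean by 0.36 SD, so 119 per group is not a planning figure.

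**What to change.** - For the randomised treatment effect, make post-partum haemoglobin, as named in Appendix 9, a continuous outcome. Analyse it by ANCOVA on enrolment haemoglobin, enrolment malaria film, the other randomised allocation and any other chosen baseline variables.
- Report the proportion below 9 g/dl beside it, also adjusted for enrolment haemoglobin, and give the same pair of measures in Appendices 7 and 9.
- Split the Appendix 7 lists into variables fixed before randomisation and variables arising after it. Reserve the delivery films for observational or explanatory analyses.
- Restate the interim claim: 474 per group within a year depends on near-complete uptake or added recruitment; about 300 to 400 is the range at 80% uptake.

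The cost is wording only, since all the data are already collected. The drawback is that a mean difference is harder to read clinically and needs the <9 g/dl result beside it.

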#### Sample size calculation: risk ratio of 2; P=0.05; 80% power.

Incidence of 1 vs 2%, e.g. pre-eclampsia; require 2514 in each group; not feasible Incidence of 5 vs 10%, e.g. postpartum anaemia, require 474 in each group; feasible for interim analysis

# **APPENDIX 8.** Procedures for handling study drugs.

### 1. FOR MOTHERS.

Identical, chewable albendazole tablets and placebo tablets will be supplied in bulk by Glaxo Smith Kline, the manufacturers.

A randomisation code will be prepared in London, and held there, by a member of the Tropical Health Epidemiology Unit of the London School of Hygiene & Tropical Medicine. A copy will be sent to Entebbe and held by a statistician who is not involved in the trial.

Albendazole or placebo and praziquantel or placebo will be packaged in consecutively numbered envelopes using the randomisation codes and these will be sealed. This will be done by two members of the MRC Programme staff who are not involved in the trial.

When mothers bring their antenatal stool samples and are enrolled in the trial they will be given the envelope in numerical order and the number on the envelope will be their study number (designated WS \_ \_ \_ \_ on data collection forms).

# 2. FOR CHILDREN.

Identical bottles of a single dose of albendazole syrup or placebo syrup will be supplied for children aged 15, 18 and 21 months. Identical chewable tablets of albendazole or placebo will be provided for children aged 24 months and above.

A randomisation code will be prepared in London, and held there, by a member of the Tropical Health Epidemiology Unit of the London School of Hygiene & Tropical Medicine. A copy will be sent to the manufacturers who will label the doses of albendazole or placebo accordingly. A full set of doses of syrup and tablets will be provided for each child, bearing the same number.

A copy of the code will be sent to Entebbe and held by a statistician who is not involved in the trial.

When children reach the age of 1 year, and consent is given for this component of the trial, they will be given the next consecutive number and they will receive the doses of medication labelled with this number.

# APPENDIX 9. PROPOSED SCHEDULE FOR ANALYSES.

# 1. PILOT STUDY.

# a. Pilot study eligibility and screening data.

Analysis period:	August 2002.
Data to be analysed:	Eligibility / socioeconomic screening data; clinical laboratory screening data.
Purpose of analysis:	To assist in design of main study and improving data collection forms.
Comment:	Unblinding not required.

# b. Pilot study screening immunological results.

Analysis period:	Approximately December 2002-February 2003
	(To begin when necessary laboratory data are complete)
Data to be analysed:	Immunological findings on samples from pilot study mothers taken at
	screening.
Purpose of analysis:	To assist in identification of immunological parameters of most interest for
	further study, and in choice of laboratory methods to be used.
	To obtain preliminary data on the effects of maternal helminth infections on
	maternal immune responses.
Comment:	Unblinding not required.

# c. Pilot study clinical and immunological findings in mothers and baby at delivery.

Analysis period:	Approximately March-May 2003.
•	(When all pilot study babies have been delivered and necessary laboratory
	data are complete).
Data to be analysed:	Clinical and laboratory (haematological, parasitological and immunological) results.
Purpose of analysis:	1. To obtain preliminary data on the effect of albendazole on outcomes at delivery, in particular:
	
 
maternal post-partum haemoglobin*
 

	• maternal and cord blood viral load in HIV-positive mothers*
	maternal parasite burden
	
 
babies' birth weight*
 

	• maternal and cord blood immune responses
	2. To examine the effect of albendazole treatment on maternal immune responses by comparing findings at enrolment and delivery in treated and untreated groups.
	3. To make preliminary comparisons between maternal and cord blood immune responses.
	4. To assist in the design of further nested studies within the cohort.
Comment:	Access to unblinded data required. **

# d. Pilot study clinical and immunological findings in babies at one year.

ratory
gical)
/ear,
•

- babies' growth\* •
- babies' immune responses to selected antigens.

This data will allow us to obtain preliminary information for comparison with earlier studies on the effects of maternal helminth infections on the response to immunisations in the babies, extending the results to new helminth species. We will also obtain preliminary data on the effects of maternal treatment for helminths.

Comment: Access to unblinded data required. \*\*

# 2. MAIN STUDY.

Comment:

#### a. Clinical findings in mothers and baby at delivery.

Approximately October 2003-January 2004. Analysis period: (When enrolment to the study has completed one year). Clinical and laboratory (haematological and parasitological) results. Data to be analysed: Purpose of analysis: To obtain preliminary data on the effect of albendazole and praziguantel on outcome at delivery for mother and baby, in particular: • maternal post-partum haemoglobin maternal and cord blood viral load in HIV-positive mothers •

- maternal parasite burden •
- eclampsia/ pre-eclampsia\*
- maternal deaths\*
- babies' birth weight
- congenital abnormalities\*
- stillbirths and early neonatal deaths\* •

Access to unblinded data required. \*\*

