#### Mothers: at delivery.

A second blood (20 ml), urine and stool sample will be obtained at delivery, before the mother leaves hospital. The blood samples will be used to perform a full blood count (for assessment of post-partum anaemia) a malaria slide and studies of the maternal immune response. The urine sample will be used as part of the assessment of pre-eclampsia and eclampsia. The stool sample will be used to determine the presence of persisting helminth infections, and to guide treatment in the case of *Strongyloides*. A placental smear will also be examined for malaria. Mothers found to have malaria will be treated.

After delivery, participants will be taken home if possible, to ensure follow up.

Mothers who receive the study drugs but do not deliver the baby in the hospital will be followed up at home to determine the outcome of the pregnancy.

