#### Interventions and exposures.

Aims 1 & 2. To examine the effects of maternal infection with intestinal nematodes or schistosomiasis, and of the treatment of maternal nematode infection or schistosomiasis in **pregnancy.** Mothers will be randomised to receive albendazole or placebo and praziguantel or placebo during the second to third trimester of pregnancy. A marked reduction in IFN-y response after BCG immunisation has been demonstrated for children of mothers with schistosomiasis or filariasis but the effects of intestinal nematodes, and the effects of treatment of helminths in pregnancy, including both intestinal nematodes and Schistosoma sp, are not known. We will determine the effect of intestinal nematodes by comparing children of mothers with and without intestinal nematodes during pregnancy (Appendix 4). If intestinal nematodes have an effect similar to schistosomiasis or filariasis, treatment of all or any of these groups of helminths in pregnancy may be beneficial for the response to immunisation in the neonate. This will be determined for individuals known to have had helminths before treatment, and for all participants (Appendix 4). If, however, treatment leads to an increase in type 2 bias, as has been documented in studies for schistosomiasis (Appendix 1, Figure 3), suppression of the neonatal type 1 response may be increased. For the same reason, treatment in pregnancy may have benefits, or disadvantages, for the neonate's susceptibility to bacterial or viral infections. For vertical transmission of HIV infection, treatment in pregnancy may have benefits for the immune response, or may enhance vertical transmission through a transient rise in viral load (Appendix 1, Figure 1). Thus, for our objectives, a randomised trial of treatment in pregnancy is appropriate. Other considerations are as follows. Treating hookworm in pregnancy can reduce anaemia,  so women with hookworm and severe anaemia will be excluded from randomisation and treated. Treating helminths may improve the mother's general health, and hence birth outcome (stillbirths, perinatal deaths, birthweight), but this has not been demonstrated in controlled trials; and there is a possible risk of teratogenicity, but this may be confined to the first trimester. Therefore, although these outcomes are not the main issue for this study, they will be recorded and considered in an interim analysis.

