#### **APPENDIX 10. Serious Adverse Events.**

A serious adverse event will be defined as any clinical event considered by the clinician to be severe or life-threatening, or that results in death. This includes events that require unexpected hospitalisation or prolongation of existing hospitalisation or results in persistent or significant disability or incapacity.

For the purposes of this study, severe adverse events include, but are not limited to: miscarriage, intrauterine death, stillbirth, neonatal death, major congenital abnormality; maternal death or death of the infant/ child; anaphylaxis, severe acute bronchospasm, seizures occurring within 24 hours of administration of the study drug.

Maternal deaths will only be reported as "serious adverse events" if they occur during pregnancy and the puerperium (within 42 days of the end of pregnancy) since no further study intervention will be given to the mothers after the treatment of helminth infections found at delivery. However, death of the mother will be documented if it occurs at any time during follow up of the child.

The likelihood of a causal association between administration of the study drug and a serious adverse event will be defined using definitions adapted from WHO terminology, as follows:

- 1. **Probable:** A clinical event, including laboratory test abnormality, with a reasonable time sequence to administration of the drug, unlikely to be attributed to concurrent disease or other drugs or chemicals.
- 2. **Possible:** A clinical event, including laboratory test abnormality, with a reasonable time sequence to administration of the drug, but which could also be explained by concurrent disease or other drugs or chemicals.
- **3.** Unlikely: A clinical event, including laboratory test abnormality, with a temporal relationship to drug administration that suggests that a causal relationship to administration is unlikely. Other drugs, chemicals or underlying disease provide a plausible explanation.
- 4. Not assessable: A clinical event for which the information received is insufficient to allow reasonable assessment.

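### Miscarriage is collected as a serious adverse event but is named in no planned comparison between arms, and nothing defines its boundary with stillbirth

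*Protocol*

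**What the plan says.** Appendix 10 lists among the reportable events "miscarriage, intrauterine death, stillbirth, neonatal death, major congenital abnormality". Miscarriage, intrauterine death and stillbirth are thus three separate categories. This is the only place in the protocol where miscarriage is mentioned.

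The outcome lists are narrower:

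- *Interventions and exposures*, Aims 1 & 2, speaks of "birth outcome (stillbirths, perinatal deaths, birthweight") and says of these and possible teratogenicity that "they will be recorded and considered in an interim analysis".
- Appendix 7, *Outcomes at delivery*, gives five birth measures: major congenital defect, stillbirth, perinatal death, low birthweight and very low birthweight. The loss endpoint that it sizes is stillbirth plus early neonatal death.
- Appendix 9, main study, analysis (a), the unblinded look at both drugs, concerns "outcome at delivery for mother and baby, in particular" a list whose only loss items for the baby are "stillbirths and early neonatal deaths".

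Appendix 7 starts the second trimester at 14 weeks, and Appendix 3 places randomisation after 14 weeks. Appendix 7 defines perinatal death through stillbirth but gives no gestational age at which a loss becomes a stillbirth. For women who took study drug and deliver elsewhere, *Mothers: at delivery* says they "will be followed up at home to determine the outcome of the pregnancy".

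**The concern.** Losses soon after a second-trimester dose are those most likely to be recorded as miscarriage. They are relevant to drug safety in pregnancy, which the protocol treats as open: it raises possible teratogenicity, says little is known about praziquantel in pregnancy, and relies on its interim analyses to judge risks and benefits. The loss endpoint that it defines and sizes begins at stillbirth, at an age it does not state.

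Two things are at stake. A treatment effect confined to early loss would not show in the loss endpoint as named. And stillbirth, birthweight and neonatal death can be observed only in pregnancies that continue, so a difference in early loss changes which pregnancies enter those comparisons. The undefined boundary adds a third problem: the same mid-pregnancy loss could be put in the compared category or in the one that is not compared.

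**Working it through.** **1. Places compared.**

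| Place in the Protocol | Loss outcomes named | Miscarriage? |
|---|---|---|
| Appendix 10 (reporting) | miscarriage, intrauterine death, stillbirth, neonatal death | yes |
| Interventions and exposures, Aims 1 & 2 | stillbirth, perinatal death | no |
| Appendix 7, measures | stillbirth, perinatal death | no |
| Appendix 7, sample size | stillbirth + early neonatal death | no |
| Appendix 9, pilot (c) | none | no |
| Appendix 9, main (a) | stillbirth, early neonatal death | no |
| Appendix 9, main (b) | neonatal and infant mortality | no |

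Intrauterine death has the same gap unless it is meant to fall under stillbirth, which is not said.

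**2. The plan's own figure.** Inputs from Appendix 7: 2% vs 4%, P = 0.05, 80% power, stated n = 1239 per group. Let d = p2 − p1 and p̄ = (p1 + p2)/2.

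- Uncorrected n = [1.960·√(2p̄(1−p̄)) + 0.842·√(p1(1−p1) + p2(1−p2))]² / d² = [1.960·√0.0582 + 0.842·√0.0580]² / 0.0004 ≈ 1141.
- Continuity-corrected n = (n/4)·[1 + √(1 + 4/(n·d))]² ≈ 1239.

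The stated figure is reproduced, two-sided with continuity correction. The same method gives 2515 for 1% vs 2% (stated 2514), 219 for 10% vs 20% and 474 for 5% vs 10%. No stated number is wrong. The point is what the endpoint contains.

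**3. Illustrative power for miscarriage alone.** The protocol gives no miscarriage rate after dosing, so control rates of 1%, 2% and 3% are assumed. The cohort of 2500 gives about 1250 per arm in each factorial comparison, assuming equal allocation. Uncorrected power = Φ{[d·√n − 1.960·√(2p̄(1−p̄))] / √(p1(1−p1) + p2(1−p2))}. For 2% vs 4% this is (0.7071 − 0.4728)/0.2408 = 0.973, so power is about 0.835.

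| Assumed doubling | Excess losses per 1250 | Power, 1250 per arm | n per arm by the plan's corrected method |
|---|---|---|---|
| 1% vs 2% | 12.5 | 0.539 | 2515 |
| 2% vs 4% | 25 | 0.835 | 1239 |
| 3% vs 6% | 37.5 | 0.952 | 814 |

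At an assumed 0.5% vs 1%, power is 0.305. So the full cohort could show a doubling only if miscarriage after dosing is about 2% or more.

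**4. A total-loss endpoint.** Add the assumed miscarriage rate to the plan's 2% for stillbirth plus early neonatal death.

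- If every component doubles, the required n per arm falls from 1239 to 814, 602 or 474 (miscarriage 1%, 2% or 3%).
- If only miscarriage doubles, power for the total at 1250 per arm is 0.274, 0.631 or 0.861. That is below the power for miscarriage alone in step 3.

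The total therefore does not always gain power. Its merits are completeness and independence from the cut-off, and its components need to be shown.

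**5. Possible distortion.** At 2% vs 4%, 25 and 50 of 1250 pregnancies would end in miscarriage, leaving 1225 and 1200. The denominators would differ by 25/1225, about 2%, which is small. The larger effect, if any, depends on whether the pregnancies lost early were also at higher risk of stillbirth or low birthweight. The documents give nothing from which to size that, or its direction.

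**The case against.** A reader might infer that miscarriages would go uncounted, or could never be compared by arm. The documents do not support that. Appendix 10 sends each serious adverse event report to the DMEC statistician, who may consult the committee and alert the Trial Steering Committee's chairman to consider an interim analysis or stopping. Appendix 9 gives the DMEC the full data set and the analysis programmes. The list in main analysis (a) is introduced as non-exhaustive, and a separate analysis plan might tabulate these events. All of this stands.

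What it does not remove is that the DMEC route is discretionary and no comparison by arm is set down for it. Nor does Appendix 7, which carries no non-exhaustive wording, include miscarriage in its measures or in the endpoint that it sizes.

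A reader might also infer that stillbirth and birthweight results would look better in a treated arm, because early losses leave the denominator. The protocol states no denominators, and the direction is not determined. Distortion is possible but not shown.

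Finally, the power figures might be read as the trial's power at the look in question. They are end-of-study figures on assumed rates. Main analysis (a) is planned after one year of enrolment, and there the protocol itself marks stillbirths and early neonatal deaths as likely to be underpowered. Dosing also extends into the third trimester, so some women will be past the period when a loss would be called miscarriage.

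**Conclusion.** The point holds as a gap in the named endpoint. Miscarriage is reportable, and study drug can be given early enough for it to follow dosing. But it is absent from the birth-outcome measures, from the sized loss endpoint and from the planned arm comparison at delivery, and its boundary with stillbirth is undefined. This does not show that harm would be hidden, since the events are collected and the DMEC can see them.

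The size cannot be fixed from the documents. On assumed rates of 1% to 3% and about 1250 per arm, a doubling would mean roughly 13 to 38 excess losses outside the named endpoint. End-of-study power to detect it would be about 54% to 95% without continuity correction, and lower at the interim look. The change is worth making because it is cheap and gives a safety endpoint that does not depend on the pregnancy continuing or on an unstated cut-off.

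**What to change.** In Appendix 7 (birth-outcome measures), in Appendix 9 main analysis (a), and for the analysis at the end of the study, add one outcome: total pregnancy loss after randomisation (miscarriage, intrauterine death or stillbirth) plus early neonatal death. Compare it by albendazole arm and by praziquantel arm, with all randomised pregnancies as denominator. Report miscarriage and stillbirth as components, and keep birthweight as its own outcome. State the gestational cut-off used to classify a loss as miscarriage or stillbirth, and how a twin pregnancy with one loss is counted, since twins are eligible.

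The cost is appendix wording and one extra table. Most of the data are already collected through serious adverse event reports and home follow-up. Two limits remain. Some losses will have uncertain dates, which affects the components but not the total. And home follow-up is stated only for women who received study drug, so the outcome of any woman randomised but not dosed must also be sought. No dose or clinical rule is affected.
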